STUDY OBJECTIVES AND HYPOTHESES

Primary objective: To evaluate the efficacy of reduced form CoQ10 (ubiquinol) supplementation in severely burned adult patients in the mitigation of MODS between 72 hours after burn injury and 12 weeks, death, or discharge (whichever comes first).

Primary objective hypothesis: Reduced form CoQ10 supplementation will result in a statistically significant reduction in the incidence of MODS between 72 hours after burn injury and 12 weeks, death, or discharge (whichever comes first) as compared to placebo.

Secondary objectives: To evaluate the effect of reduced form CoQ10 (ubiquinol) supplementation in severely burned adult patients on the following clinical outcome events and biochemical measurements in plasma and urine between 72 hours after burn injury and 12 weeks, death, or discharge (whichever occurs first):

1. The six individual organ systems comprising the MODS score and their times of occurrences,
2. The weighted composite score of the six constituents
3. The maximum total Sequential Organ Failure Assessment (SOFA) score
4. The maximum SOFA score for each organ
5. AUC of total SOFA score (score x days)
6. AUC of SOFA score for each organ (score x days)
7. Delirium (CAM-ICU) (number of days)
8. Length of hospital stay (number of days)
9. Sepsis (Sepsis-3) (number of incidence)
10. Septic Shock (Sepsis-3) (number of incidence)
11. Plasma mitochondrial DNA (4 blood collections)
12. 3-Methylhistidine (3-MH) and creatinine in urine (a biomarker of muscle wasting)

Secondary objective hypothesis: Reduced form CoQ10 supplementation will result in a statistically significant reduction in each of the secondary endpoints between 72 hours after burn injury and 12 weeks, death, or discharge (whichever comes first) as compared to placebo.

RESEARCH DESIGN

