1	Increase in serum creatinine (SCr) by $\geq 0.3\text{mg/dL}$ within 48 hours or increase in SCr 1.5 to 1.9 times baseline which is known or presumed to have occurred within the prior 7 days
2	Increase in SCr to 2.0 to 2.9 times baseline
3	Increase in SCr to 3.0 times baseline or increase in SCr to $\geq 4.0\text{ mg/dL}$ or initiation of renal replacement therapy

ARDS: ARDS is a common complication in critically ill burn patients leading to increased mortality. The American European Consensus Conference (AECC) ARDS definition was revised by the Berlin definition in 2012 (**Table 4**). Since then, the ARDS Berlin definition has been used in critically ill patients⁵⁹, including wartime military burns⁶⁰. We will use the ARDS Berlin definition in this study.

Table 4. The ARDS Berlin Definition	
	Oxygenation
Mild	$200\text{mmHg} < \text{PaO}_2/\text{FiO}_2 \leq 300\text{mmHg}$
Moderate	$100\text{mmHg} < \text{PaO}_2/\text{FiO}_2 \leq 200\text{mmHg}$
Severe	$\text{PaO}_2/\text{FiO}_2 \leq 100\text{mmHg}$

Cardiovascular dysfunction: To assess cardiovascular dysfunction, we will use the sequential organ failure assessment (SOFA) scores (**Table 5**). The SOFA score is a simple and objective score that allows for calculation of both the number and the severity of organ dysfunction in six organ systems (e.g., respiratory, coagulation, liver, cardiovascular, renal), and the score can measure individual or aggregate organ dysfunction⁶¹ and has been used in many previous studies in critically ill patients, including burn victims. Cardiovascular dysfunction is a common complication of severe burn injury. CoQ10 deficiency causes and/or exacerbates heart failure and clinical trials have shown the protective effects of CoQ10 supplementation in chronic heart failure.

Coagulopathy: Severe burn injury is associated with systemic coagulopathy, which is characterized by procoagulant changes, as well as impaired fibrinolytic and endogenous anticoagulation systems⁶²⁻⁶⁵. The exact pathophysiology of burn-induced coagulopathy is incompletely understood, but recent studies indicate that circulating mtDNA and mitochondrial damage can induce hypercoagulopathy and thrombocytopenia⁶⁶⁻⁶⁸. It is conceivable, therefore, that CoQ10 supplementation may ameliorate coagulopathy by mitigating mitochondrial dysfunction/disintegrity in burn patients.

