Scientific rationale for the observation period: Studies in trauma patients have suggested the organ dysfunction that develops soon after trauma (i.e., during the first 48 -72 h) rapidly resolves in a high proportion of patients and may reflect the reversible derangement of organ function induced by the inciting event or incomplete resuscitation. Thus, it has been proposed that later assessment of organ function (i.e., 3 days after injury) will yield a more accurate definition of multiple organ failure in trauma patients, which is needed to evaluate the relationship between trauma-induced organ dysfunction and prognosis^{71,72}. In the acute phase, particularly the first 72 hours after severe burn injury, organ dysfunction frequently occurs, causing AKI (e.g., oliguria), cardiovascular dysfunction (e.g., hypotension), and coagulopathy (e.g., thrombocytopenia)⁷³. In some cases, the organ dysfunction is transient and the patient may recover during the late-acute or sub-acute phase. In such cases, the recovery from organ dysfunction is associated with relatively good prognosis. In contrast, if the organ dysfunction continues beyond the acute phase or if it occurs or recurs at a later time, the clinical outcome is typically worse. Therefore, we will evaluate the effects of

CoQ10 supplementation on the aforementioned multi-organ dysfunction that patients encounter beginning 72 hours post-burn injury and thereafter.

Secondary endpoints: Secondary endpoints will be the following outcome events observed from 72 hours after burn injury through 12 weeks or until death or discharge (whichever occurs first) and the biochemical measurements in plasma and urine.

1. The six individual binary outcome MODS events and their times of occurrences, (i.e., the constituents of the primary composite score)
2. Weighted composite score of the six constituents
3. Maximum total SOFA score
4. Maximum SOFA score for each organ
5. AUC of total SOFA score (score x days)
6. AUC of SOFA score for each organ (score x days)
7. Delirium (CAM-ICU) (number of days)
8. Length of hospital stay (number of days)
9. Sepsis (Sepsis-3) (number of incidence)
10. Septic Shock (Sepsis-3) (number of incidence)
11. Plasma mitochondrial DNA (4 blood collections)
12. 3-Methylhistidine (3-MH) and creatinine in urine (a biomarker of muscle wasting)

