Data Analysis: For between-arm comparisons of single valued (either measured at once or as an aggregated variable such as AUC over a period) outcomes, we will apply chi-square test if the outcome is binary, and *t*-test or Mann-Whitney *U*-test to continuous outcomes based on the best fit of Shapiro-Wilk's test. The between-arm difference in the distributions of times to the first event and multiple events (of the six constituents) will be examined by using single event time Cox's model and the times to correlated multiple events using Cox's model allowing multivariate frailty, respectively. The incidence rates of each individual event, with- and without differentiating its severity, as a binary outcome will be compared between the two arms by means of longitudinal logistic modeling with generalized estimating equation (GEE)⁸⁴ to allow more than one events per patient. For the repeated measures analysis of the longitudinal plasma mitochondrial DNA and urine 3- methylhistidine (3-MH), we will examine if the mean levels over time are different between the two arms by using longitudinal general linear mixed effects model⁸⁵ which will provide the within group time dependency patterns as a linear effect or more complex form of non-linear patterns which would be able to characterize the time dependent treatment effects over time along with testing for time \times group interaction(s) of those model parameter(s). Total and organ-specific SOFA scores over time will also be examined by this mixed effects models of which the

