particular interest is to test if the improvement in the longitudinal mean SOFA scores is greater during certain time window. All analyses will also be extended to adjust for the influencing effects of any baseline demographic and/or clinical indications. Missing data may be unavoidable. Because the informed consent from many study enrollees will be obtained through the family members (i.e., surrogates), a small portion (up to 2% attrition rate) of the enrolled patients may voluntarily withdraw from the study. Before final analysis, we will check the missing data pattern of the outcomes first. If there are systematic differences in missing data patterns between the study groups and/or patient characteristics (e.g., burn type), we will take into account such problems in the analysis. The longitudinal mixed effects modeling will provide unbiased and consistent estimates of the effects provided that the missing data mechanism is ‘missing at random’ (MAR). If necessary, multiple-imputation will be applied to all endpoints analyses. All statistical tests will be two-sided and will adopt a 5% significance level.

Sample size calculation: The sample size of 290 study patients for this study is determined to achieve an adequate statistical power at a 5% Type-1 error rate for the primary endpoint analysis by the following statistical calculations. We first estimated the expected means and variances of the composite scores (assuming the six individual events are independent) for the Control and CoQ10 treatment arms under the assumption depicted in **Table 6** via 1000 repeated simulated data sets ($n = 5000$ each), instead of calculating them algebraically.

Each simulation run calculated the means and variances of the two arms, and the resulting average means (and variances) over 1000 simulations were 2.43 (1.04) in the placebo arm and 1.94 (1.05) in CoQ10 arm respectively. Based on the assumption about the event incidence rates and the estimated means and variances of the composite scores from the simulated data sets, the calculated required sample size per treatment arm (using PASS¹¹⁰) to detect such a difference (i.e., 20% reduction in the overall events) with 80% power at a 5% Type-1 error rate using 2-sided independent samples t-test was 142 per arm.

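### Twelve secondary endpoints, holding about 21 to 29 comparisons, are each predicted to be significant and each tested at an unadjusted 5%, with no hierarchy and no exploratory label

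*Combined protocol and SAP*

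**What the plan says.** Under Study Objectives and Hypotheses, the secondary hypothesis reads: "Reduced form CoQ10 supplementation will result in a statistically significant reduction in each of the secondary endpoints". The Secondary endpoints section then lists 12 numbered items. Three of them contain several comparisons:

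- Item 1: "The six individual binary outcome MODS events and their times of occurrences"
- Item 4: "Maximum SOFA score for each organ"
- Item 6: "AUC of SOFA score for each organ (score x days"

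The Cardiovascular dysfunction paragraph describes SOFA as measuring "severity of organ dysfunction in six organ systems", while Table 5 sets out scores for three (cardiovascular, coagulation, liver).

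The Data Analysis section gives one error rule for everything: "All statistical tests will be two-sided and will adopt a 5% significance level". It also plans further analyses of the same data. Each event is to be analysed "with- and without differentiating its severity, as a binary outcome will be compared between the two arms", and there are time-by-group interactions, an unspecified time window for SOFA, and covariate-adjusted versions of all analyses. The sample size is justified for the primary endpoint only. Nowhere does the document order the secondary endpoints, adjust for their number, or call them supportive or exploratory.

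**The concern.** Leaving secondary endpoints unadjusted is common and defensible when they are presented as supportive. Here the protocol attaches a formal prediction of significance to each one and allows each its own 5% test. If the primary result is null or borderline, nothing in the plan prevents an isolated p<0.05 on one organ, one SOFA summary or one biomarker from being presented as a predicted benefit. What is at stake is the credibility of secondary claims. The primary test is not involved.

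**Working it through.** The plan states no familywise error rate for the secondary endpoints, so there is no figure of its own to reproduce.

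**1. Count of comparisons.** Items 2, 3, 5 and 7 to 12 are one variable each, giving 9. Item 1 has six binary events (five dysfunctions and death). Items 4 and 6 have three or six organs each.

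- Three organs (Table 5): 9 + 6 + 3 + 3 = 21
- Six organs: 9 + 6 + 6 + 6 = 27
- Adding the two event-time models in Data Analysis (a Cox model for the first event and a frailty model for multiple events): 23 or 29
- Six organs, with each of the six event times tested separately instead: 27 + 6 = 33

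The severity-graded, adjusted, interaction and time-window analyses are not counted.

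**2. Error rate if no secondary endpoint is affected and the tests are independent.** For k tests, at least one p<0.05 in either direction has probability 1 − 0.95^k. At least one significant result in the predicted direction has probability 1 − 0.975^k. The expected numbers are 0.05k and 0.025k at any correlation.

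| k | Either direction | False reduction | Expected, either | Expected, reduction |
|---|---|---|---|---|
| 12 | 46% | 26% | 0.60 | 0.30 |
| 21 | 66% | 41% | 1.05 | 0.53 |
| 27 | 75% | 50% | 1.35 | 0.68 |
| 29 | 77% | 52% | 1.45 | 0.73 |
| 33 | 82% | 57% | 1.65 | 0.83 |

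**3. Correlated tests.** Event, organ maximum, organ AUC and total scores reuse the same organ data, so positive correlation is expected. The documents give no correlations, so those below are assumptions. Results come from 200,000 simulated sets of normal test statistics.

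| Assumed structure | k | Either direction | False reduction |
|---|---|---|---|
| Common correlation 0.3 / 0.5 / 0.7 | 27 | 63 / 49 / 33% | 33 / 25 / 16% |
| Common correlation 0.3 / 0.5 / 0.7 | 33 | 69 / 53 / 35% | 37 / 27 / 18% |
| Within organ 0.5–0.9, between organs 0.2–0.5 | 27 | 39–63% | 20–34% |
| Within organ 0.5–0.9, between organs 0.2–0.5 | 33 | 42–69% | 21–38% |

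The lowest values in any scenario run were 13% (either direction) and 7% (reduction), for 12 tests with a common correlation of 0.9. A single test would give 5% and 2.5%.

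**4. Is significance for each endpoint realistic?** Inputs are the Table 6 rates and 290/2 = 145 per arm. With SE = √[(p₁(1−p₁) + p₂(1−p₂))/145], power ≈ Φ(Δ/SE − 1.96) + Φ(−Δ/SE − 1.96).

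| Component | Rates | Δ/SE | Power |
|---|---|---|---|
| AKI; ARDS (each) | 40% vs 32% | 0.080/0.0562 = 1.42 | 30% |
| Cardiovascular; coagulopathy (each) | 70% vs 56% | 0.140/0.0561 = 2.50 | 70% |
| Liver | 10% vs 8% | 0.020/0.0336 = 0.60 | 9% |
| Death | 8% vs 6.4% | 0.016/0.0303 = 0.53 | 8% |

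Under the independence that the sample size section assumes, all six would be significant with probability about 0.08 × 0.09 × 0.30² × 0.70² = 0.0003.

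**The case against.** The strongest reply is that the hypothesis covers each endpoint and has a direction. Read literally, it requires success on all of them, and an all-must-succeed rule needs no adjustment. On that reading one p<0.05 confirms nothing, and a significant increase contradicts the hypothesis. This stands in part. A reader might infer that any single p<0.05 confirms the secondary hypothesis, but the documents state no such rule. They state no all-must-succeed rule either, and separate 5% tests leave individual claims open. If success on all were intended, step 4 shows that it is practically out of reach.

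A reader might also take 75% to 82% as the chance of a false claim of benefit. That is not supported. Those figures require independent tests, no effect on any secondary endpoint, and harmful-direction results counted as hits. For a false reduction, the chance under the assumed correlations is well below one half, and the expected number is below one for every count.

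The figure of 33 is also an upper reading, because Data Analysis describes two event-time models and not six tests. Finally, the primary is a single endpoint and the sample size rests on it alone. That limits the point to secondary claims.

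**Conclusion.** The point holds for the secondary endpoints. The plan predicts significance for each of 12 items and tests them all at an unadjusted 5%, so the chance of at least one false positive is well above 5% in every scenario examined. Over 21 to 33 comparisons it is 66% to 82% in either direction under independence. Under the assumed correlations it is 33% to 69% for 27 to 33 comparisons. For a false reduction the corresponding figures are 41% to 57% and 16% to 38%. All of these assume no true effect on any secondary endpoint, and the correlated figures rest on correlations that the documents do not supply.

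It would go too far to say that a false claim of benefit is more likely than not, or that the primary endpoint's error rate is inflated by this rule. The plan should be changed on this point, but the defect does not undermine the primary analysis.

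**What to change.** 1. State that the primary endpoint is the only confirmatory test.
2. Reword the secondary hypothesis so that it no longer promises significance for each endpoint.
3. Report items 1, 4 and 6, and the covariate-adjusted and time-window analyses, as estimates with 95% confidence intervals and no significance claim.
4. If formal secondary claims are wanted, apply Holm's procedure to the nine remaining items (2, 3, 5 and 7 to 12), and only if the primary is significant. Name one analysis for each. Items 11 and 12 are repeated measures and need a single named contrast. Holm over all 12 would not work, because items 1, 4 and 6 have no single p-value. Without the condition on the primary, a secondary claim could still follow a null primary result.

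The cost is a change to a protocol hypothesis as well as to the analysis text, made before unblinding. Under step 4 the smallest p-value must be below 0.05/9 = 0.0056. An endpoint with 80% power at 5% then has about Φ(1.960 + 0.842 − 2.773) = Φ(0.029) = 51% power at that first step. The mtDNA and 3-methylhistidine items come from only the first 100 subjects, so they have the least information with which to meet it. The sample size and the primary analysis do not change.

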3-Methylhistidine concentrations will be quantified by negative chemical ionization gas chromatography mass spectrometry as described in our previous studies^{52,53}. Urinary creatinine concentrations will be measured by a commercial kit. The average of three measurements on the three consecutive days at each time point will be used for statistical analysis to minimize possible day-to-day variations.

STATISTICAL ENDPOINTS AND APPROACH TO DATA ANALYSIS

This two-arm balanced double blind parallel Randomized Clinical Trial (RCT) study will be performed using an intention to treat (ITT) analysis population that includes all randomized patients.

Primary endpoint: The primary endpoint will be the count of the following events. This count will be used to create a composite score ranging from 0 to 6 by assigning 1 to each event regardless of stage, scores and severity that individual subjects encounter from 72 hours after burn injury through 12 weeks or until death or discharge, whichever occurs first:

1. Acute Kidney Injury (AKI) (KDIGO Stages 1 – 3)
2. ARDS (The Berlin ARDS Definition: Mild, Moderate, Severe)
3. Cardiovascular Dysfunction (SOFA Scores 1 – 4)
4. Coagulopathy (SOFA Scores 1 – 4)
5. Liver dysfunction (SOFA Scores 1 – 4)
6. Death (all causes)

We will calculate mean values of the composite sum scores among the study patients in the CoQ10 and placebo arms, and then test their difference by using an independent samples *t*-test if the observed data are evident to follow a normal distribution by Shapiro-Wilk's test. Otherwise, Mann-Whitney U test will be applied and the group specific medians and quartiles will be used as the summary statistics.

AKI: AKI represents the acute loss of kidney function and is associated with a profound and severe increase in morbidity and mortality in burn patients⁵⁴. Early AKI, which occurs less than 3 days post-burn, is usually related to inadequate fluid replacement during the initial resuscitation. AKI can occur later in the hospitalization and late AKI is multifactorial in origin and often associated with sepsis development⁵⁵. For the purposes of this study, we will follow the definitions and classification guidelines set forth in "AKI of Kidney Disease: Improving Global Outcomes (KDIGO)"^{56,57} (**Table 3**). Published in 2012, this guideline has been used in critically ill patients and in combat-injured populations⁵⁸.

Stage	Table 3. AKI (KDIGO)

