Liver dysfunction: Hepatic function plays pivotal roles in immune function, acute-phase response, systemic inflammatory response, detoxication, and metabolism. Burn causes dysfunction and morphological changes (e.g., hepatomegaly) of the liver⁶⁹. Although liver failure is not a frequent complication of burn injury, increased serum bilirubin level is associated with the mortality of severely burned patients⁷⁰.

	Cardiovascular System	Coagulation	Liver
SOFA Score	Hypotension	Platelets ($10^3/\mu\text{l}$)	Bilirubin (mg/dl)
1	MAP $< 70\text{ mm Hg}$	< 150	1.2 - 1.9
2	dop ≤ 5 or dob (any dose)	< 100	2.0 - 5.9
3	dop > 5 OR epi ≤ 0.1 OR nor ≤ 0.1	< 50	6.0 - 11.9

4	dop>15 OR epi>0.1 OR nor>0.1	<20	>12.0
Table 5. Cardiovascular, coagulation and liver SOFA score. MAP: mean arterial pressure; dop: dopamine; dod: dobutamine; epi: epinephrine; nor: norepinephrine. Adrenergic agents administered for at least 1 hour (doses given are in $\mu\text{g}/\text{kg}/\text{min}$).			

Note that "coma" is not included within the primary endpoint calculations, even though mitochondrial dysfunction impairs the central nervous system. The rationale for this exclusion is that precise evaluation of coma and consciousness (e.g., Glasgow coma scale) is sometimes difficult to carry out due to intubation and sedation in severely burned patients. However, delirium will be evaluated by the Confusion Assessment Method for Intensive Care Unit (CAM-ICU) as one of our secondary endpoints.

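### The 80% power stated for 142 per arm assumes independent events and does not follow from its own inputs; power should be shown over a range of correlations

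*Combined protocol and SAP*

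**What the plan says.** Under Sample size calculation, the means and variances of the composite score come from simulated data, "assuming the six individual events are independent". The results "were 2.43 (1.04) in the placebo arm and 1.94 (1.05) in CoQ10 arm respectively". From these the plan concludes that the number needed to detect a "20% reduction in the overall events" "with 80% power at a 5% Type-1 error rate using 2-sided independent samples t-test was 142 per arm". Total enrolment is 290, with attrition of up to 2% expected. The paragraph gives no correlation between events and no sensitivity analysis.

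Other sections treat the six components as linked:

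- Scientific rationale for the primary endpoint: mitochondrial dysfunction is presented as a cause shared by heart, kidney, lung, liver and platelets, and multi-organ dysfunction as a main driver of death.
- Data Analysis: the times of the multiple events are to be modelled as correlated, with a multivariate frailty Cox model.
- Primary endpoint: AKI "is associated with a profound and severe increase in morbidity and mortality in burn patients"; "ARDS is a common complication in critically ill burn patients leading to increased mortality"; and "increased serum bilirubin level is associated with the mortality of severely burned patients".

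**The concern.** The variance of a sum of events is the sum of their variances plus twice the sum of their covariances. Independence sets every covariance to zero. If the events cluster within patients, as the endpoint rationale implies, the standard deviation of the score exceeds the one used for planning, and power for a given difference is lower. The primary comparison would then rest on a power figure calculated for a narrower distribution than the trial will observe. A reader could not tell from the paragraph which reduction the trial can detect.

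**Working it through.** **Inputs.** Table 6 rates, placebo / CoQ10: AKI 40/32%, ARDS 40/32%, cardiovascular 70/56%, coagulopathy 70/56%, liver 10/8%, death 8/6.4%. Two-sided alpha is 0.05, power 80%, allocation 1:1. The correlation is not in the documents; the range 0 to 0.4 is an assumption.

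**1. The plan's own figure.** n per arm = 2 × variance × (1.960 + 0.842)² / difference², where (1.960 + 0.842)² is about 7.85.

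- Stated inputs (average variance 1.045, difference 2.43 − 1.94 = 0.49): 2 × 1.045 × 7.85 / 0.2401 = 68.3, so 69 (70 by t-test).
- Bracketed figures read as standard deviations: 72 (73 by t-test).
- Exact Table 6 values (means 2.380 and 1.904, difference 0.476; variances, as the sum of p(1−p), 1.064 and 1.062): 2 × 1.063 × 7.85 / 0.2266 = 73.6, so 74 (75 by t-test).

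None gives 142. Neither does 90% power (92-99), 95% power (114-122) or alpha 0.01 (102-110). Two explanations come close. One is that 142 is a total (2 × 69 = 138 or 2 × 72 = 144). The other is that the two variances were added and used as the common variance (137 from the stated inputs, 148 from Table 6). The documents do not settle which. The 290 does treat 142 as per arm: 142 / 0.98 = 144.9, so 145 per arm.

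At 142 per arm under independence, t-test power is 98% with the stated inputs and 97% with Table 6.

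**2. Adding correlation.** With average pairwise correlation phi:

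variance = Σp(1−p) + phi × [(Σ√(p(1−p)))² − Σp(1−p)]

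Placebo: 1.064 + 5.025 phi. CoQ10: 1.062 + 4.901 phi.

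| Average phi | Variance, placebo / CoQ10 | SD | Power at 142 per arm | n per arm for 80% | Detectable reduction |
|---|---|---|---|---|---|
| 0 | 1.064 / 1.062 | 1.03 | 97% | 74 | 14% |
| 0.1 | 1.566 / 1.552 | 1.25 | 89% | 109 | 17% |
| 0.2 | 2.069 / 2.042 | 1.43 | 80% | 143 | 20% |
| 0.3 | 2.571 / 2.532 | 1.60 | 71% | 177 | 22% |
| 0.4 | 3.074 / 3.022 | 1.75 | 63% | 212 | 24% |

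Power is from the t-test at a difference of 0.476; n is from the normal approximation. Detectable reduction = 2.80 × SD × √(2/142) / 2.38. At phi 0.3, for example, 2.80 × 1.597 × 0.1187 / 2.38 = 22%.

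**3. Break-even.** Power of 80% at 142 per arm allows a variance of 142 × 0.476² / (2 × 7.85) = 2.05, so phi = (2.05 − 1.063) / 4.963 = 0.199 (0.196 by t-test). With the stated difference of 0.49 it is about 0.22. At 145 per arm it is about 0.205 to 0.233, depending on the difference and the approximation.

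**4. Attainable range.** For two events with rates a < b, the largest possible phi is √[a(1−b) / (b(1−a))]. For death (8%) with a 70% event this is √(0.024/0.644) = 0.193. A phi of 0.2 therefore cannot hold for every pair and must be read as an average. The largest simple average over all pairs is about 0.49 in the placebo arm and 0.53 in the CoQ10 arm.

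**5. Cross-check.** A latent-Gaussian model that keeps the Table 6 rates gives an average phi of about 0.10, 0.20 and 0.30 at latent correlations of 0.2, 0.4 and 0.6. The t-test falls below 80% at an average phi of about 0.19. Simulated Mann-Whitney power at 145 per arm is about 89%, 81% and 72-73% at those latent correlations.

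**The case against.** The strongest reply is that the planned number already absorbs moderate correlation. At 142 per arm the variance can roughly double, from 1.06 to 2.05, before power drops below 80%. This stands. However, the protocol does not present the margin as an allowance for correlation, and the margin exists only because 142 is about twice what the stated inputs require.

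A second reply concerns the evidence. The quoted statements on AKI, ARDS and bilirubin link organ events to death, which is rare here. Setting those three death pairs to the largest covariance the rates allow gives variances of 1.40 and 1.35 and power of 93%; doing so for all five organ-death pairs gives 91%. This also stands: the mortality links alone cannot bring power below 80%. Substantial organ-to-organ correlation is needed. The endpoint rationale and the frailty model support its presence but give no size.

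Three stronger readings are tempting and should be resisted:

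- A reader might infer that the trial is underpowered. The documents do not show that average phi exceeds 0.20.
- A reader might treat 0.4 as being as plausible as 0.1. It lies close to the attainable maximum.
- A reader might infer that a null result could not be interpreted. The test uses the observed variance, so the planning assumption does not disturb the type I error rate, and the confidence interval will show which effects are excluded.

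**Conclusion.** The point holds in a limited form. Independence is stated openly but is at odds with the protocol's own rationale and analysis model, and the single 80% figure is not supported. It is too low under the stated inputs, and it is too high if average phi exceeds about 0.20 to 0.23. Over the assumed range, power runs from 97% down to 63%. These figures rest on the Table 6 rates, a uniform 20% reduction in every component, and a correlation range that the documents do not supply. The defect lies in the stated justification of the sample size; inadequate enrolment has not been demonstrated.

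**What to change.** In the Sample size calculation section:

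1. Show how 142 per arm was obtained from the stated means and variances, or correct it. Do not simply adopt a correlation of 0.20 because it happens to return 80%.
2. Rerun the simulation with correlated events that respect the Table 6 rates, and state the source of any assumed correlation. The 30-patient pilot is a weak source: it admitted burns from 5% TBSA, with group means of 19.4% and 13.9%, whereas this trial enrols 20-70%.
3. Replace the single 80% with power and detectable reduction at 145 per arm (142 after 2% loss) for average phi from 0 to 0.4, for both the t-test and the Mann-Whitney fallback.

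The cost is one simulation and a reworded paragraph. Enrolment, endpoint and analysis stay as they are. The drawback for the sponsor is that one power figure becomes a range, part of which may be less favourable.
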